Protocol Number:

Video-Assisted Speech Technology-003

Protocol Date and Version #:

2/28/23 - version #3

Study Title

Video Assisted Speech Technology to enhance functional language abilities in individuals with Autism Spectrum Disorder

Investigators (including sub-investigators)

[name], M.A. CCC-SLP/CAS

[name], M.S. CCC-SLP/CAS

Address / Phone - Contact details

[name]

[name]

Source of external funding

National Institutes of Health (NIH)

Hypothesis

Users of the VR integrated VAST application will show improved functional language abilities and oral motor coordination skills.

Background

Autism Spectrum Disorder (ASD) is a neurodevelopmental communication disorder resulting in functional language and behavioral delays affecting over 3.5 million Americans. These delays vary with the severity of symptoms that present in ASD. Individuals may be verbal and possess stronger functional language abilities whereas 25% of people in the ASD population are minimally verbal or non-verbal, having increased communication challenges. ASD limits many aspects of speech such as vocabulary acquisition where the individual retains a limited lexicon. This restriction on word choice leads to further limitations in the development of sentence structure. Conversation is kept to simple requests and commands and only basic topics are maintained for discussion, preventing the expression of abstract ideas. Alongside linguistic acquisition, oral-motor coordination is a crucial part of speech production. Students with ASD struggle with acquiring the necessary motor skills needed for speech articulation and activities such as chewing.

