Aim 1: Develop a beta product VR-based VAST platform. Currently, the alpha product VAST program utilizes filmed mouths enunciating words and phrases in a 2D setting. Developers will code the VR mouths and the graphic design for all linguistic elements. Coding will comprise of C++ & Unreal Engine 4 where unreal engine utilizes a node-based language called *Blueprints Visual Scripting*. Further attributes of Unreal Engine include a skeletal animation system combined with higher polygon models. In addition to VR programming, the *Dolch Vocabulary list* will be integrated into the system as a base word list consisting of frequently used English words. Within the list are 220 easily recognizable service words including nouns and non-nouns which target the kindergarten-through-third grade age group. *Deliverable: The alpha product 2D software will be developed into a 3D VR environment to ensure maximum optimization of the product for client use.*

Aim 2: Develop hardware prototype. We will compare the utility of combining off-the-shelf VR goggles & Bone Conduction (BC) headphones with a 3D printing of a single cohesive unit. The strength of the BC headphones will be tested alongside standard headphones to determine if they provide optimal functionality. After testing each option, the product with the highest rate of efficacy will be used to create the integrated prototype. *Deliverable: Functional hardware prototype.*

4.2.c. Interventions

Type	Name	Description
Behavioral (e.g., Psychotherapy, Lifestyle Counseling)	VR-based VAST platform	The VR-incorporated prototype, 3D video-modeled VAST application
Behavioral (e.g., Psychotherapy, Lifestyle Counseling)	2D video modeling	VAST application using 2D video recordings and no hardware prototype

Aim 3: Demonstrate feasibility of VR-based VAST platform. We will pilot test the VR VAST app on 6 children with ASD. The recruited population will consist of 6 ASD children between the ages of 4 and 8 who will be recruited to participate in a 14-sessions-long study that will utilize the VR-integrated VAST application. The subjects will each receive a different piece of equipment: one group of five will receive a 3D VR-integrated VAST prototype, while the other group of five will receive a 2D VAST on a tablet. Sessions will be held twice a week with each lasting approximately 30 minutes (i.e. 30 minutes +/- 5 minutes).

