Three main metrics will be measured during the pilot study: *Percentage of Correctly Transcribed Words Using ASR, Articulation Accuracy, and Mean Length of Utterance (MLU)*. These metrics will show whether there has been improvement in the participant’s functional language abilities, and oral motor coordination skills. They will be

analyzed by several trained staff members who will observe each recorded and monitored session.

Subject Selection

Recruiting: Subjects will be recruited by contacting (e.g. email or telephone) teachers and professionals (e.g. speech-language pathologists and behaviorists) who work with children with autism, aged 4 to 8. The research team will reach out to school administrators, teachers, and specialists through the iTherapy network of contacts to recruit eligible K-2 students diagnosed with ASD and their teacher or specialist. The VR-based VAST platform is designed for use with early elementary school-aged students (grades K-2). In order to conduct the intervention and gather data that would be useful for further development of the product, the research study must include early elementary school students.

In order to recruit enough children within the study's target population and to encourage retention, the study team will use online advertising via social media and other platforms (e.g. Craigslist) to reach participants. All participants will be given an Apple device (iPhone 6 for VR or refurbished iPad mini for 2D) for participating in the study and a free download of InnerVoice (valued at \$99.99), an iOS AI-powered communication app that uses video self-modeling, designed and sold by iTherapy.

Number of participants: 6

Inclusion/Exclusion criteria: All participants will be recruited via campaigns posted on social media and/or other platforms: parents/guardians will be provided consent forms and all information regarding inclusion/exclusion criteria.

Children **under the age of 18** will be recruited and all protections mandated by NIH policy afforded to them.

In order to protect participants and their families from COVID-19 exposure, participants will undergo Aim 3's procedures within their homes: the subjects' data will be collected using a HIPAA-compliant telehealth video-streaming platform. The goal of this

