procedure is to minimize any potential exposure to infection as a result of participating in this study. The study's team will follow CDC-recommended cleaning and disinfection guidelines to ship and retrieve the prototype VR headset (that is, the bone-conduction headphones along with the goggles sans the iPhones, which the participants can keep as part of participating in the study).

The proposed study will not discriminate based on gender, sexual orientation or race. Participants will be recruited from a pool of children at participating clinics and educational facilities independent of the above-mentioned aspects. There are no exclusion criteria based on gender, sexual orientation, or race.

Because data prior studies strongly support no significant differences of clinical or public health importance in intervention effect between subgroups, then sex/gender and/or race/ethnicity will not be recorded as subject selection criteria.

Children with a medically documented history of seizure disorder will be excluded from the study. According to Carnegie Mellon University Entertainment Technology Center (2019), individuals with a history of seizure disorder should avoid using virtual reality media.

Study procedures / research method

Due to health and safety concerns associated with the COVID-19 pandemic, the feasibility procedures will be conducted through a HIPAA-compliant telehealth platform. The subjects' caregivers or parents will help measure the impact of two pieces of technology: the 3D VR-integrated headset with bone-conduction and the 2D tablet-based application.

In order to prevent the spread of pathogens among large groups of subjects, the number of participants has been reduced from 30 to 10. Ten ASD students between the ages of 4 and 8 will be recruited to participate in a 14-sessions-long study that will utilize the integrated VAST application. The subjects will each receive a different piece of technology: one group of five will receive a 3D VR-integrated VAST prototype, while the other group of five will receive a 2D VAST version on a tablet. Sessions will be held twice a week with each lasting approximately 30 minutes (i.e. 30 minutes +/- 5 minutes).

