Three primary metrics and three secondary metrics will be examined during the pilot study: **Change in Percentage of Correctly Transcribed Words Using Automatic Speech Recognition (ASR), Change in Articulation Accuracy, Change in Mean Length of Utterance (MLU), Parent Perceptions of Communication Changes Resulting from Study Participation, Change in Type-Token Ratios, and Change in Response Rate to Treatment Stimuli.** The frequency and duration of sessions is

based on our extensive previous research and is intended to ensure a statistically relevant number of data points to measure the learning progress of the students.

Impact will be measured via the following:

Change in Percentage of Correctly Transcribed Words Using Automatic Speech Recognition will be used as a measure of speech intelligibility. Specifically, the closed-captioning ASR on the Google Meet teleconferencing platform will be used as pre- and post-test measures to assess whether an individual has changed their ability to accurately articulate the target words. A higher percentage of correctly transcribed words will indicate articulatory accuracy and will provide a calculation of speech development rate. Due to the COVID-19 pandemic, distance learning will likely be a supplementary or primary medium of service delivery for children on the autism spectrum. Therefore, rating intelligibility on teleconferencing platforms may serve as a functional measure that could reflect subjects' communicative aptitude within a new social environment (i.e. distance learning).

Change in Articulation Accuracy will be calculated by two speech-language pathologists (SLP) transcribing the subjects' spoken production of the target words. Both SLPs will calculate the change in % of correct phonemes in each attempted stimulus by determining the correct number of phonemes in each of the subject's production of the target words.

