Change in Mean Length of Utterance (MLU) – participants (aged 4 to 8 years) will be given a pre- and post-test 15-minute language sample. MLU was calculated for tests and gain from pre-test to post-test was compared. This measure is calculated based on a change in the number of morphemes per utterance during pre-test and post-test language samples. During a five-minute period, two licensed speech-language pathologists (SLP) will observe a parent interacting and talking with their child. Both will SLPs transcribe the subjects' speech and calculate a mean length of utterance (MLU) for each subject. MLU will be calculated by determining how many bound and free morphemes are included within every spoken utterance produced by a subject. The total number of morphemes produced within the 5-minute period will be divided by total number of utterances, which will then produce the MLU for each subject. This procedure will be used for determining MLU in both the pre- and post-testing procedures.

Parent Perceptions of Communication Changes Resulting from Study Participation – this measure examined parent observations and perceptions of changes in their children's motor-speech, behavioral, and social communication skills after having participated in the study.

Change in Type-Token Ratios – type-token ratio measures the total number of unique words in a given segment of language. The goal of using this metric is to examine any change in lexical diversity following either the tablet- or VR-based treatment.

Change in Response Rate to Treatment Stimuli – Response rate gain will be measured to determine whether there are any significant changes in how often children responded to pre- and post-testing stimuli after having received treatment between the iPad Pro and VR goggles groups.

Each session will be monitored and recorded. Two members of the trained staff will then observe these videos and analyze the rates of the aforementioned metrics.

Outcome Measures

Type	Name	Time Frame	Brief Description

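### The plan states no rule for allocating children to VR or 2D and no masking of scorers to device or time point, leaving both the pre-to-post change and the VR-versus-2D contrast open to avoidable bias

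*Combined protocol and SAP*

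**What the plan says.** **Aim of the comparison.** The Hypothesis section reads "Users of the VR integrated VAST application will show improved functional language abilities and oral motor coordination skills", a statement about change in VR users. Outcome Measures adds comparisons both within and across groups for the automatic speech recognition (ASR) outcome, and a comparison of the two device groups for response rate. Statistical Design and Power plans a between-group ANOVA that includes MLU.

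**Allocation.** Aim 3 says "The subjects will each receive a different piece of equipment". Study procedures says "one group of five will receive a 3D VR-integrated VAST prototype, while the other group of five will receive a 2D VAST version". Neither these nor any other section says how a child comes to be in one group. The total is also unsettled: Subject Selection has "Number of participants: 6", Study procedures has ten, and Aim 3 pairs six children with two groups of five.

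**Scoring.** All of this is in Study procedures.
- Articulation accuracy: "Both SLPs will calculate the change in % of correct phonemes in each attempted stimulus".
- MLU: "two licensed speech-language pathologists (SLP) will observe a parent interacting and talking with their child", after which both transcribe and calculate.
- Metrics generally, from the session recordings: "Two members of the trained staff will then observe these videos and analyze the rates of the aforementioned metrics".

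No section states that any scorer is kept unaware of device or of time point.

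**The concern.** Phoneme accuracy and morpheme counts depend on human judgement. A scorer who expects the session 14 sample to be better can, without intending it, produce change in the hypothesised direction when speech has not changed. Having two scorers does not protect against an expectation that both share.

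Separately, if assignment is not random, a difference between VR and 2D may reflect which children went into which group. Intended Use of Data says the results will be used to examine whether the VR system helps, so both weaknesses bear on a conclusion the sponsor means to draw.

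**Working it through.** The plan has no figure of its own on this point. The check is a reading of what each scorer would know, followed by short algebra and the arithmetic of the remedy.

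**1. What each scorer would know if the plan is followed as written**

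| Outcome | Scored by | Time point | Device |
|---|---|---|---|
| Articulation accuracy | Two SLPs, who also compute the change | Known; a change cannot be computed otherwise | Not stated |
| MLU | Two SLPs observing parent and child; can be read as live | Known if live | Not stated |
| Metrics scored from recordings | Two trained staff viewing each recorded session | Known if sessions are viewed in order | Probably known after viewing treatment sessions |
| ASR words | Captioning software, though Outcome Measures also mentions transcription by a speech pathologist | Depends on the part the pathologist plays | Same |
| Parent perceptions | Parent | Known | Known |

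The device entry for the recording reviewers is an inference. Sessions 1 and 14 are reserved for testing, and nothing says that the device is visible in them.

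**2. Which comparison each kind of knowledge affects.** Let the scoring bias in a child's change be b(VR) in one arm and b(2D) in the other. Let s be the difference in expected change that arises from who was assigned where.
- Bias in the within-arm change for VR users: b(VR).
- Bias in the VR-minus-2D contrast: b(VR) − b(2D) + s.
- If scorers know only the time point and b(VR) = b(2D) = b, the within-arm bias is b and the scoring part of the contrast is b − b = 0.
- If scorers know the device, b(VR) and b(2D) can differ and the difference does not cancel.
- Selective allocation enters through s for every outcome, ASR included.
- With two scorers who share the bias, the average is (b + b)/2 = b, so double scoring leaves it unchanged.

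**3. What randomisation would and would not do.** It makes the expected value of s zero. The standard error of a chance difference in prognosis, in SD units, is √(2/n) with n per arm: √(2/3) = 0.82 for 3 and 3 (an assumed even split of 6), and √(2/5) = 0.63 for 5 and 5.

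**4. Why group totals must be fixed.** Unrestricted 1:1 assignment gives 5 and 5 among 10 children with probability 252/1024 = 25%, and 3 and 3 among 6 with probability 20/64 = 31%. Study procedures calls for five and five.

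**5. Volume of masked scoring.** Two recordings per child gives 2 × 6 = 12 or 2 × 10 = 20. The documents give both a 15-minute sample and a 5-minute MLU window:
- at 15 minutes, 180 or 300 minutes (3 or 5 hours) per scorer;
- at 5 minutes, 60 or 100 minutes (1 or 1.7 hours) per scorer.

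These are running times. Transcription takes longer.

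**The case against.** **Silence is not proof.** A reader might infer that scorers are in fact unmasked, or that the results are biased. The documents do not support that: they state no masking, which is weaker than stating that there is none. The text also refers to sections that do not appear in it under those names, so it may come from a fuller application. What stands is that the written workflow works against masking, most plainly where the SLPs compute the articulation change themselves.

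**Steered allocation.** A reader might infer that family preference or tolerance of the headset decides who gets VR. Nothing says so. The remark in the ethics section on differing stimulation thresholds explains why children are monitored for discomfort; it is not about assignment. Likewise, the leftover template question about independent analysis in Data Management is not evidence about masking.

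**It is a small feasibility pilot.** True, and the between-group result is exploratory under any allocation method. But the protocol states an efficacy hypothesis and intends to use the data to examine benefit.

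**It may already be done.** Parts of Study procedures and Outcome Measures are in the past tense. If allocation is complete, that part of the fix becomes disclosure; recorded samples can still be rescored.

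**Masking would not rescue the pre-to-post claim.** This is correct and should be said openly. The parent is the conversation partner in the MLU sample and knows both device and time point. There is no untreated arm, so maturation, practice and the existing therapies that continue alongside the study also affect change.

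**Conclusion.** The point holds as an omission that should be corrected. No allocation rule and no masking are stated, and the plan as written gives scorers knowledge of time point for articulation, probably for MLU, and probably knowledge of device for those who review all sessions. Time-point knowledge threatens the within-child change and largely cancels between arms if it acts equally in both. Device knowledge and selective allocation threaten VR versus 2D. The ASR outcome is less exposed to scoring bias but equally exposed to allocation.

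The size of any bias is unknown, and no figure for it can be drawn from the documents. The conclusion rests on reading silence as not stated, and on the inference that staff who watch the treatment sessions learn the device. A reader might go further and conclude that random allocation and masked scoring would make the efficacy claim secure. They would remove two avoidable biases; the limits set by parent elicitation, the lack of an untreated arm and 3 to 5 children per group would remain.

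**What to change.** **(a) Allocation.** If it is still to come, first reconcile the total of 6 with the total of 10. Then assign children from a concealed, computer-generated list, blocked so that the groups are equal (5 and 5 if the total is 10). If allocation has happened, state the method and, if it was not random, label VR versus 2D a non-randomised contrast.

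**(b) Scoring.** Score every human-scored outcome from the session 1 and session 14 recordings: articulation accuracy, MLU, type-token ratio, response rate, and any SLP transcription used for the ASR measure. Use random codes shuffled across children, arms and time points. Existing SLPs can score, with a team member who does not score holding the code. Where possible, scorers should not have run or reviewed those children's sessions. Trim cues to device or date, and compute change by script after scores are locked. If scoring was done unmasked, rescore this way and report both sets.

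**(c) Reporting.** Report parent perception as unmasked. State that masked scoring does not remove parent elicitation effects, nor maturation, practice or concurrent-therapy effects, and that the between-group result is exploratory.

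**Separate point.** Reconcile the articulation rate named in Statistical Design and Power with the articulation accuracy in Study procedures and Outcome Measures before assuming that a between-group test of accuracy is planned.

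**Cost.** No extra children or assessments. The work is coding and trimming 12 or 20 recordings and naming a code holder. If rescoring is needed, add transcription time, which will exceed the 1 to 5 hours of running time per scorer. Masking will be imperfect if voices are recognised among 6 to 10 children.

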Primary	Change in Percentage of Correctly Transcribed Words Using Automatic Speech Recognition	Seven weeks--each subject participated in the study twice a week over a 7-week period for a total of 14 sessions. The first and last sessions (session #1 and session #14) were reserved for pre-test and post-test language sample collection and assessment.	15-minute pre- and post-testing was performed using speech recognition software and transcribed by a licensed speech pathologist. Differences pre- and post-intervention were compared across groups and within groups.
Primary	Change in Articulation Accuracy	Seven weeks--each subject participated in the study twice a week over a 7-week period for a total of 14 sessions. The first and last sessions	Change in % of correct phonemes in each attempted stimulus

		(session #1 and session #14) were reserved for pre-test and post-test language sample collection and assessment.	
Primary	Change in Mean Length of Utterance (MLU)	Seven weeks--each subject participated in the study twice a week over a 7-week period for a total of 14 sessions. The first and last sessions (session #1 and session #14) were reserved for pre-test and post-test language sample collection and assessment.	Participants (aged 4 to 8 years) were given a pre- and post-test 15-minute language sample. MLU was calculated for tests and gain from pre-test to post-test was compared.
Secondary	Parent Perceptions of Communication Changes Resulting from Study Participation	Seven weeks--each subject participated in the study twice a week over a 7-week period for a total of 14 sessions. The first and last sessions (session #1 and session #14) were reserved for pre-test and post-test language sample collection and assessment	Parent observations -- perceptions of changes in their children's motor-speech, behavioral, and social communication skills after having participated in the study

Secondary	Change in Type-Token Ratios	Seven weeks--each subject participated in the study twice a week over a 7-week period for a total of 14 sessions. The first and last sessions (session #1 and session #14) were reserved for pre-test and post-test language sample collection and assessment.	A type-token ratio measures the total number of unique words in a given segment of language.

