There are no events that would preclude a participant from continuing the intervention beyond withdrawal of assent or consent. As detailed in the Protections Against Risk above, the study presented no greater than minimal risk to participants. Trials will be stopped upon any visual observance of discomfort of the participant by the educator or trained professional (as detailed in the Protections Against Risk above). Data will be reported from all sites upon session completion – compliance and monitoring will be ensured by an on-site researcher who will collect session data. Further data security measures are detailed above in Collaborating Sites.

Any IRB and/or ISM/DSMB actions will be reported to the NIH within 72 hours of occurrence by the project PI [name].

Study Oversight

Data and safety will be monitored per NIH guidelines by project PI and IRB. Individual responsible for monitoring are:

1. [name] (project PI). [name] will ensure data security on a bi-weekly basis. Her position as CEO of iTherapy will include the monitoring of all data acquired from this study. She will ensure that all staff are adequately trained in the study protocol.
2. [name] (Co-Investigator). [name] will ensure safety on-site on a weekly basis. As the Chief Operations Officer at iTherapy, he is qualified to ensure data and safety during data collection.
3. IRB will ensure protocol adherence to acceptable safety practices.

Data Management

[Who will be collecting, analyzing the data? Do you plan to have an independent data analysis? Data retention (i.e. how long so you plan to maintain records for this study). Include statistical analysis plan (if applicable)]

Data formats — data will be stored in commonly-used file formats (e.g., .csv for survey data, .mp3 for audio files, .mov for screen recordings). There are no applicable metadata standards that will be applied to these data.

Dissemination — all data generated in this SBIR Phase I project is considered proprietary. A project report will be made available partial and/or aggregated form, upon request, to the intervention developers. A subset of the project report will be made available, upon request, to partner school districts or other organizations who assisted in recruiting participants.

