the activities at any time for any reason. Children will be asked for verbal consent. Participants will be informed that they can stop the sessions at any time for any reason. Because of the varying stimulatory thresholds of those with ASD, participants will be closely monitored by their teachers or health professionals for any visual or verbal sign of discomfort. Should any sign be observed, the participant's session will immediately be ceased.

Confidentiality

The confidentiality of all participants will be maintained throughout the life of the project, and the research team will institute and monitor robust data security protocols. All members of the research team will complete an online course covering research with human subjects and data security prior to the study's commencement. Data will be collected and stored on a secure online server. A code key will be created to assign a unique number to each study participant (i.e. P001). The data collected in this study will in no way be affiliated with the participants' medical record number or personnel files. All participant data will be stored on a secure, encrypted data storage device and/or a password protected and encrypted internet- or cloud-based storage system, which meets HIPAA privacy standards. The files will also be password encrypted. No data will be accessible from any source that is not password encrypted. The password will only be known to IRB-approved research study members.

Intended Use of Data

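### The seven-week frame and session #14 agree only with full attendance, and no post-test is planned for a child who stops treatment sessions early

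*Combined protocol and SAP*

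**What the plan says.** The time-frame cell is essentially the same for all six outcomes in the Outcome Measures table. It opens with a calendar period and a session count: "Seven weeks--each subject participated in the study twice a week over a 7-week period for a total of 14 sessions". It then assigns the tests: "The first and last sessions (session #1 and session #14) were reserved for pre-test and post-test language sample collection and assessment". The body of the protocol gives the same frequency (Study procedures / research method): "Sessions will be held twice a week with each lasting approximately 30 minutes".

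Five of the six outcomes are changes from pre-test to post-test. For mean length of utterance (MLU) the table says: "MLU was calculated for tests and gain from pre-test to post-test was compared". The sixth, parent perceptions, is collected after participation and is not a pre/post difference.

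On stopping, the section IRB Review / Ethics / Informed Consent says: "Participants will be informed that they can stop the sessions at any time for any reason". The section on monitoring adverse events says: "There are no events that would preclude a participant from continuing the intervention beyond withdrawal of assent or consent".

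The documents give no visit window, no statement on whether missed sessions are made up, no assessment after early stopping, no analysis set and no missing-data rule. Statistical Design and Power names an ANOVA between groups and does not mention the test interval.

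**The concern.** A gain needs two tests. If the only post-test is tied to session #14, whether a child contributes to the analysis depends on staying in treatment to the end.

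The protocol itself gives a reason why staying may not be independent of arm. Risk / Safety Information foresees frustration or fatigue from the sensory content of the treatment and describes sensory overload as common in these children. One group wears goggles with bone-conduction headphones and the other uses a tablet, so stopping because the headset is not tolerated can happen in one group only. A comparison of those who remain could then favour the device that lost its least successful users.

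The loss is also partly avoidable. Testing takes place at home over telehealth. As described, the MLU sample is a parent talking with the child while two speech-language pathologists observe, and the intelligibility measure uses teleconference captions. Neither description requires the child still to be using the device.

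**Working it through.** **Inputs from the documents.** Two sessions per week for 7 weeks; tests at sessions 1 and 14. Group size is five per arm under Study procedures / research method (total 10). Subject Selection instead has "Number of participants: 6", which is three per arm if split equally (assumption). Both sizes are carried through. No dropout or attendance figures are given, so every scenario below is an assumption.

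1. **The plan's schedule.** 2 × 7 = 14 sessions, which reproduces the stated figure. With full attendance session #14 falls in week 7 and the two anchors agree. Sessions 1 and 14 are for testing, leaving 14 − 2 = 12 treatment sessions.

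2. **A child who stops early.** A child who stops after session 6, say, has a pre-test but no session #14. Gain = post − pre is undefined, and no rule supplies a value or another test date.

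3. **Effect on an arm's mean gain.** Assume one of n children would have gained 0 and the others each gain g. The mean over all children is g(n − 1)/n; the mean over completers is g.
   - n = 5: g / 0.8g = 1.25, overstated by 25%.
   - n = 3: g / 0.667g = 1.50, overstated by 50%.

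   A milder version: the lost child would have gained D SD less than the others' mean. The arm's mean is then overstated by D/n. For D from 0.5 to 1.5 SD this is 0.10 to 0.30 SD with n = 5 and 0.17 to 0.50 SD with n = 3. If the other arm loses nobody, the between-arm difference shifts by the same amount.

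4. **Effect on precision, whatever the reason for loss.** 95% half-width for a difference in means, in SD units = t(0.975, a + b − 2) × √(1/a + 1/b).

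| Arms | Half-width (SD) |
|---|---|
| 5 v 5 | 1.458 |
| 4 v 5 | 1.586 (+9%) |
| 3 v 3 | 2.267 |
| 2 v 3 | 2.905 (+28%) |

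5. **Chance of losing at least one child** = 1 − (1 − d)^N, for an assumed dropout probability d.

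| d | N = 10 | N = 6 |
|---|---|---|
| 5% | 40% | 27% |
| 10% | 65% | 47% |
| 20% | 89% | 74% |

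6. **A child who misses sessions but continues.** At even half-week spacing (assumption), session 1 to session 14 spans 13 × 0.5 = 6.5 weeks. The documents leave two readings open.
   - Missed sessions are made up at the end at two per week: four missed add 2 weeks, and 2 / 6.5 = 31% more elapsed time.
   - Missed sessions are skipped: the interval stays at 6.5 weeks, and four missed leave 12 − 4 = 8 treatment sessions.

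**The case against.** Three stronger readings are tempting, and the documents support none of them.

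- **A reader might infer that the post-test has no calendar anchor.** It has one: the same table cell sets a seven-week period. The gap is that nothing says which anchor governs when the two diverge.
- **A reader might infer that a child who misses sessions is tested later.** That holds only if missed sessions are made up, which the documents do not say. The 31% figure rests on that reading and on an assumed four missed sessions.
- **A reader might infer that the result is biased.** No attendance or dropout data are given. Loss unrelated to gain costs precision only. The between-arm contrast is biased only if loss is related to gain and differs by arm. The 25% and 50% figures describe one arm's mean gain under a severe assumption.

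Other objections have some force. The sentence on stopping sessions stands among sentences about halting activity in progress, so it may partly concern a single session. The only stated route out of the intervention is withdrawal of assent or consent, and some of those children would refuse the test too, so the number recovered is unknown. An early post-test is not planned, but it is not ruled out either. The protocol aims to encourage retention and gives families a device and an app. Finally, testing after a set course of sessions is a legitimate target for a feasibility pilot, so for children who merely miss sessions the choice between calendar time and session count is a trade-off.

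None of this supplies a post-test for a child who stops treatment but could still be tested. The plan never separates stopping sessions from declining the test.

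**Conclusion.** The point holds in limited form. Followed literally, the plan yields a gain analysis of children who reach session #14, in arms of three to five. That carries a risk of bias in the VR-versus-2D contrast if stopping relates to benefit or tolerance and differs by arm, and a loss of precision otherwise.

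Its size depends on assumed dropout. One lost child who would have gained nothing overstates that arm's mean gain by 25% (five per arm) or 50% (three per arm), and the milder scenario gives 0.10 to 0.50 SD. Losing one child for any reason widens the confidence interval by 9% or 28%. These figures show how sensitive the design is; they do not estimate what happened or will happen.

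**What to change.** Change the time-frame text in the Outcome Measures table to say, in substance: *every child with a session-1 test is offered the post-test at about week 7, including a child whose treatment sessions have stopped, unless consent to the test itself is withdrawn.* Give the window around week 7.

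In Statistical Design and Power, state that all tested children are analysed in the arm they were given. Report for each child the number of sessions delivered and the interval between tests, and for each arm the number without a post-test. State also whether missed sessions are made up. A week-7 test evens out the interval but leaves session counts unequal, so both need to be recorded.

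The cost is a wording change and, for each child who stopped, a telehealth call that was already planned. The downside is that some children are tested after fewer than 12 treatment sessions. The estimate is then the effect of offering the device and may be slightly smaller.

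The outcome table is written largely in the past tense. If data collection is already complete, what remains is to report test dates, sessions delivered and children without a post-test, by arm.
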